15.1. Ethics committee and regulatory authorities

The Clinical investigation plan and/or other relevant documents are submitted to the appropriate EC. This clinical investigation will not begin until the required approval from the EC have been obtained. Any amendment to the pro-protocol will be submitted to the same EC.

Sponsor will notify the relevant regulatory authority and EC concerned of the end of the clinical investigation.

15.2. Other relevant authorities

E.g. Data Protection Agency: Clinical Regulatory Department in Coloplast A/S has obtained a general approval from the Danish Data Protection Agency to handle data collected in a clinical investigation.

15.3. Data protection

As part of the investigation Coloplast A/S, [name] ("Coloplast") will collect and process the personal information the subject provides for the investigation ("subject personal data"). This includes identification and contact information (which may be anonymised depending on the nature of the investigation) as well as information about product usage experience and your health. Coloplast will comply with the EU General Data Protection Regulation (GDPR) and the Danish act on data protection ("databeskyttelsesloven"), including in connection with transfer of data to third countries, cf. chapter V of GDPR, Coloplast will only process the subjects' personal data:

1. To conduct the investigation and carry out related research based on subject consent (primary use), cf. articles 6(1)(a) and 9(2)(a) of GDPR,
2. To comply with applicable legal obligations to e.g. ensure reliability and safety, cf. article 6(1)(c) in conjunction with article 9(1)(i) of GDPR, and
3. If separate consent is given for secondary use of subject personal data, cf. articles 6(1)(a) and 9(2)(a) of GDPR – carry out research outside the clinical protocol to improve Coloplast's products and services, and for use in education.

Part of Coloplast's processing is carried out on third-party platforms (clinical trial databases) and certain third parties are assisting Coloplast in the processing (e.g. the investigator). Such cases will imply a transfer of your personal data to the third parties, but solely for the specified purposes and with the third parties acting on instruction from Coloplast. Data may be collected and processed across the Coloplast network, which may entail processing of personal data outside the European Economic Area. In such cases, an adequate level of protection will be ensured by the third parties being subject to the standard contractual clauses on data protection adopted by the EU or to an EU-approved certification mechanism on data protection. For further information about this please the subject can always consult Coloplast's data protection officer (details below).

Subject personal data will be kept as long as required under applicable laws and regulations. The EU Medical Device Regulation obligates Coloplast to keep the data for a period of at least ten years after the investigation is completed, or, in the event that the device is subsequently placed on the market, at least ten years after the last device has been placed on the market. Subject personal data will be deleted at the end of the mandatory retention period.

If the subject has questions or queries regarding Coloplast's handling of personal information, the subject can always contact Coloplast's Data Protection Officer at [contact]. Complaints related to Coloplast's handling of subject personal information may similarly be sent to the Data Protection Officer, and the subject is also entitled to file a complaint with the relevant supervisory authority, which in the case of Denmark is the Danish Data Protection Agency (www.datatilsynet.dk).

The subject can write to [contact] at any time to request:

- Access to personal data
- Correction of errors in personal data or to erase personal data
- Limit what can be done with personal data
- To receive personal data in machine-readable format (data portability).
- Withdrawal of consents the subject has given Coloplast to process personal data

15.4. Indemnity

All subjects are fully covered by Coloplast A/S insurance throughout the investigation.

15.5. Financial conditions

Coloplast A/S will compensate the Principal investigator involved in the clinical investigation for his time and resources spent on the investigation. All financial agreements with the Principal investigator involved in the clinical investigation will be specified in the sponsor investigator agreement.

The expenses include the salary to the Principal Investigator, the cost of external clinical support, investigation supplies, eCRF, Investigator and site personnel training.

The Principal Investigator and site personnel have no financial interests in the investigation.

The total budget for the investigation is covering 67 participants. The expenses are paid on an ongoing basis.

16. Informed consent process

Written informed consent is obtained from all subjects participating in the investigation after thorough written and verbal information. The information is given by the investigator or his/her representative in the subjects' native non-technical language. Each subject will be fully informed about the aim of the investigation, procedures, potential risks, or inconveniences and/or expected benefits, all anticipated adverse device effects and then have a minimum of 24h before deciding on participation. The subjects will be informed, that their participation is voluntary and that they may leave the investigation at any time, without this having any influence on their further treatment.

The informed consent signature form includes personally dated signatures of the subject and the PI or his/her representative responsible for conducting the informed consent process. A copy will be provided to the subject.

If new information is to be given during the investigation, sponsor will inform the investigators, and the new information is given to the subjects by the investigator. If new information becomes available that can significantly affect a subject's future health and medical care that information will be provided to the subject in written form. CM is responsible for writing the information and providing the approved Subject Information and

Consent Form to investigators that will further provide it to the subjects. If applicable, all affected subjects shall be asked to confirm their continuing informed consent in writing.

17. Subject compensation

17.1. Compensation in case of injury

Product liability and No-Fault Clinical Investigation Insurance covering the duration of the clinical investigation are in place, to enable compensation in the event of an injury to a participating subject, see section 15.4.

17.2. Compensation for participating in the clinical investigation

Subjects will not be financially compensated for their time but may benefit from prevention of a sacral pressure ulcer.

18. Adverse events, adverse device effects and device deficiencies

18.1. Adverse events

An adverse event is any untoward medical occurrence, unintended disease or injury, or untoward clinical signs (including abnormal laboratory findings) in subjects, whether or not related to the investigational medical device(s) or the comparator(s), or the procedures involved. The adverse event shall be marked with the intensity mild, moderate or severe. This could include events such as headache or dizziness.

18.2. Adverse device effect

An adverse event, which is related to the use of the investigational medical device, is an adverse device effect, and should be marked as unlikely related, possible related, probable related or with causal relationship on the adverse event form.

The definition of an adverse device effect includes any event resulting from insufficiencies or inadequacies in the instruction for use, deployment, implantation, installation and operation, or any malfunction of the medical device, as well as any event resulting from use error or from intentional misuse of the device.

Table 6 lists anticipated adverse device effects that may occur, based on the IFU and their likely incidence rates based on adverse events reported in clinical studies⁴.

Table 6

ANTICIPATED ADE	INCIDENCE RATES
Local pressure injury/Erythema*	1-10%
Skin irritation/inflammation/itching	0.1 %-1%
Maceration and/or local fungus infection of the skin	0.01-0.1%
Pain	0.01-0.1%
Blistering	0.01-0.1%
Allergic skin reaction	Not known

* *Temporary redness/erythema upon removal of the sacral bandage is not considered an adverse device effect, however an abnormal development in intensity or duration should be considered as such.*

18.3. Device deficiency

A device deficiency is the inadequacy of the investigational medical device or comparator with respect to its identity, quality, durability, reliability, usability, safety or performance. This includes malfunctions, use errors

Only in cases, where rolling edges are observed more than normal, it should be registered as a device deficiency.

18.4. Serious adverse events (SAE)

A serious adverse event is an adverse event that:

- Led to death,
- Led to a serious deterioration in the health of the subject, users or other persons as defined by one or more of the following:
 - 1) a life-threatening illness or injury, or
 - 2) a permanent impairment of a body structure or a body function including chronic diseases, or
 - 3) in-patient or prolonged hospitalization, or
 - 4) medical or surgical intervention to prevent life-threatening illness or injury or permanent impairment to a body structure or a body function.
- Led to foetal distress, foetal death, a congenital abnormality or birth defect including physical or mental impairment.

This includes device deficiencies that might have led to a serious adverse event if:

- 1) Suitable action had not been taken, or
- 2) Intervention had not been made, or
- 3) Circumstances had been less fortunate.

These are handled under the serious adverse event reporting.

Planned hospitalization for a pre-existing condition, or a procedure required by the CIP, without serious deterioration in health, is not considered a serious adverse event.

18.4.1. Serious adverse device effect (SADE)

A serious adverse device effect is an adverse device effect that has resulted in any of the consequences characteristic of a serious adverse event.

18.4.2. Anticipated serious adverse device effect (ASADE)

Anticipated serious adverse device effect is any effect that by its nature, incidence, severity or outcome has been previously identified in the risk analysis report.

18.4.3. Unanticipated serious adverse device effect (USADE)

An unanticipated serious adverse device effect is a serious adverse device effect which by its nature, incidence, severity or outcome has not been identified in the current version of the risk analysis report.

18.5. Medical care of subjects

Principal Investigator shall ensure that adequate medical care is provided, during and after participation in the clinical investigation, to a subject experiencing an adverse event. All ongoing ADEs, SAEs, SADEs and DDs, that could have led to a SAE at subject termination, will be followed according to the Risk Benefit analysis (see 8.2) An ongoing adverse event at subject termination visit is documented as the current status for the adverse event and will not be followed up.

The subjects shall be informed of any new significant findings occurring during the clinical investigation, including the need for additional medical care that can be required, and of the nature and possible cause of any adverse events experienced

Principal Investigator shall provide the subject with the necessary instructions on proper use, handling storage and return of the investigational device and comparator, when it is used or operated by the subject.

18.6. Reporting and timelines

18.7. Investigator's reporting responsibilities

- PI at each site must assess all (S)AE's that occur at his/her site.

- All serious adverse events and serious adverse device effects must be reported to sponsor within 24 hours of the site becoming aware of the event.
- A device deficiency that could have led to a serious adverse event but did not because suitable action was taken, intervention had been made or because of fortunate circumstances should be reported to sponsor within 24 hours of the site becoming aware of the event.
- New findings and/or updates in relation to already reported serious events should also be reported to sponsor within 24 hours of the site becoming aware of the event.
- Device deficiencies and all adverse device effects related to CE marked Coloplast investigational product and/or comparator must be reported to sponsor within 24 hours of becoming aware of the event.

When reporting the SAE, the relationship to the test material shall be described whether the event is considered

- **Not related**, the event has no temporal relationship with the use of the test material or the procedures.
- **Unlikely related**, the relationship with the use of the test material seems not relevant and/or the event can be reasonably explained by another cause, but additional information may be obtained.
- **Possible related**, the relationship with the use of the test material is weak but cannot be ruled out completely. Alternative causes are also possible (e.g. an underlying or concurrent illness/ clinical condition or/and an effect of another device, drug or treatment). Cases were relatedness cannot be assessed or no information has been obtained should also be classified as possible.
- **Probable related**, the relationship with the use of the test material seems relevant and/or the event cannot reasonably be explained by another cause, but additional information may be obtained.
- **Definitely related/Causal relationship**, the event has a temporal relationship with the test material use/application or procedures.

and the intensity of the event should be considered, as such:

- **Mild**, the intensity of the event is mild with no further action or intervention
- **Moderate**, the intensity of the event will lead to an action or intervention to solve the event
- **Severe**, the intensity of the event will lead to follow up on the action or intervention, as the effect of the action or intervention may not decrease the symptoms.

All above events must be reported by use of the relevant adverse event/serious adverse event/device deficiency form.

Please report to:
 Coloplast A/S
 [name]
 [name]
 Denmark

[contact] and [contact]

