4.5. Handling of the investigational device

The subjects will be included for up to 7 days.

Subjects that are included in the investigation and applied the investigational product, are expected to wear the product up to 7 days or until discharged. The same product will be applied for the entire test period, however if necessary, due to contamination or rolling edges, the product must be replaced with a new product.

Therefore, the subjects are expected to use approximately 1 product, however the site will be supplied with enough products in case of replacements of products for the duration of the investigation.

In total 67 subjects will be enrolled. To allow for unpredicted dressing changes, 1 patient requires 7 heart shaped/small products, which is per 67 patients: $67 \times 7 = 469$ small sacral products.

Around 30 patients may need the large sacral bandage: $30 \times 7 = 210$ large sacral products.

5. Design of the clinical investigation

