7.1. Clinical investigation-related procedures

Screening Visit (V0), Day 0:

- Introduction to the investigation and review of Subject information Form
- Check of in- and exclusion criteria
- Informed Consent Form – ICF signed at Visit 0. If subject wishes to have time for consideration, it is possible and the ICF is signed at Visit 1 the following day
- Inclusion in investigation and allocation of subject number after ICF is signed

Baseline Visit (V1), Day 1:

- Introduction to the investigation and review of Subject information Form
- ICF signed (if not signed at Visit 0)
- Confirmation of inclusion and exclusion criteria if more than 24 hours has passed since Visit 0
- Collect baseline information:
 - Gender (male/female)
 - Age (at time of enrollment (years)
 - Height (cm)
 - Weight (kg)
 - Urinary incontinence (Y/N)
 - Faecal incontinence (Y/N)
 - Date and main reason for admission (e.g., diabetes mellitus, cardiovascular disease, renal disease, pulmonary disease, anaemia, trauma, other)
 - Skin inspection
 - Braden Scale Score
- Apply Biatain Silicone Bandage on the sacral area

Baseline 2-7, skin inspection, Day 2-7:

- Partial lift of test product and skin inspection for signs of non-blanchable erythema over bony prominence/sacral pressure injury over bony prominence

- Re-application of the test product
- Has there been a test product change (Y/N)?
 - if yes, please register what the cause of the change was (dressing soilage, weakened border, damp/saturated dressing, bulky foam, other)

Termination Visit 8, Day 8 or at the day of discharge/earlier termination date:

- Have signs of non-blanchable erythema over bony prominence/sacral pressure injury over bony prominence developed (Y/N)?
 - If yes, please specify stage of pressure injury (*Appendix 3*)
- Was there any non-compliance to the local pressure injury prevention guideline (Y/N)?
 - If yes, explain non-compliance
 - if yes, please include a summary in the comment page

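### Section 18.7 defines the top and bottom SAE causality grades by timing alone, and no section says which grades make an event device-related

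*Combined protocol and SAP*

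**What the plan says.** Section 18.7 introduces the scale for serious events: "When reporting the SAE, the relationship to the test material shall be described whether the event is considered". Five grades follow. *Not related* means that "the event has no temporal relationship with the use of the test material or the procedures". *Definitely related/Causal relationship* means that "the event has a temporal relationship with the test material use/application or procedures". Between them, *Unlikely related* applies when the link seems irrelevant and/or "the event can be reasonably explained by another cause, but additional information may be obtained". *Possible related* covers a weak link that is not excluded, and *Probable related* a relevant link or the lack of another reasonable explanation.

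Section 18.2 defines an adverse device effect (ADE) as an adverse event related to use of the device. It says such an event is to be marked with one of four grades, the lowest being *unlikely related*. It does not define those grades. Under 18.4.1 a SADE is an ADE with serious consequences. Under 18.4.3 a USADE is a SADE that the current risk analysis report does not identify.

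On exposure, 4.5 says: "The same product will be applied for the entire test period", with replacement if it is soiled or its edges roll. The test period is up to 7 days or until discharge. Section 7.1 prescribes for days 2 to 7: "Partial lift of test product and skin inspection for signs of non-blanchable erythema". Table 5 in 7.2 adds the same step at the termination visit.

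**The concern.** The study has one arm, its aim is device safety, and its subjects are ill enough to be in hospital. Serious events from the underlying illness are to be expected, and there is no concurrent control group to set them against. The causality grade is then the recorded item that separates an event of the illness from an event of the device.

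If the two ends of that scale rest on timing, and nearly all observed time is wear time, the grade cannot do this work. An SAE caused by the illness can be recorded as definitely caused by the dressing, and none with onset during wear can be recorded as unrelated. SADE and USADE status is built on relatedness, and 9.1.3 asks the sponsor to ensure that unanticipated adverse device effects are found and investigated quickly. Genuine ones could be mixed with events of the illness.

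**Working it through.** No figure in the plan rests on this point, so there is nothing to recompute. The check sets the definitions side by side.

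**Step 1: what decides each grade in 18.7**

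| Grade | Deciding criterion | Role of timing |
|---|---|---|
| Not related | No temporal relationship | Sole criterion |
| Unlikely related | Link seems irrelevant and/or another explanation exists | Not mentioned |
| Possible related | Weak link, not excluded; alternatives allowed; also used when the link cannot be assessed | Not mentioned |
| Probable related | Link seems relevant and/or no other reasonable explanation | Not mentioned |
| Definitely related/Causal | Temporal relationship present | Sole criterion |

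Nothing says that the top grade includes the criteria of the grades below it, that the grades exclude one another, or which to take when two apply.

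**Step 2: apply them to one event.** Take an SAE with onset on day 3, dressing in place, for which the admitting illness is a reasonable explanation.

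- It arose during use of the test material, and Table 5 has a partial lift and skin inspection at each visit from V2 until termination. Both end grades refer to procedures as well as the material. A temporal relationship exists, so *Not related* is unavailable.
- Another cause explains it, so *Unlikely related* is met.
- A temporal relationship exists, so *Definitely related* is also met.

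One event thus qualifies for two grades with opposite meanings. An investigator who applies the wording of the top grade and one who applies its label can grade it differently, and both can point to the plan.

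**Step 3: from grade to ADE, SADE and USADE.** No section says which grades count as device-related. Two kinds of cut-off can be considered.

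- *Every grade except Not related counts.* This fits the list in 18.2, which is the 18.7 list without *Not related*. The overlap in step 2 then does not matter, since both grades give an ADE. The narrow definition of *Not related* does matter: essentially every SAE during wear becomes an ADE, and so a SADE.
- *The cut-off lies above Unlikely related.* This fits the sentence in 18.2 that an ADE is a related event. The overlap then does matter: the day-3 event is a SADE if graded *Definitely* and not if graded *Unlikely*.

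The wording fails under either cut-off, by a different route. A SADE of this kind is also a USADE if the risk analysis report does not identify it.

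**Step 4: what does not depend on the grade**

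- The primary endpoint (5.2) is the number of adverse events, and 18.1 counts them whether or not related.
- The secondary endpoint (5.3) is the number of device deficiencies.
- SAE reporting to the sponsor: "All serious adverse events and serious adverse device effects must be reported to sponsor within 24 hours" of the site becoming aware.
- Ongoing SAEs are followed after termination (18.5), and all SAEs go to the authorities (18.8).

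**Step 5: non-serious events.** The 18.7 scale is introduced for SAEs, and whether its definitions also serve 18.2 is not stated. The missing cut-off reaches non-serious events in any case, because 18.7 says that "all adverse device effects related to CE marked Coloplast investigational product and/or comparator must be reported to sponsor within 24 hours". Section 18.5 also follows ongoing ADEs after termination but not other ongoing non-serious events. Whether a non-serious *unlikely related* event falls under these rules cannot be read from the plan.

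**The case against.** The strongest reply is that the scale works in practice. The top grade carries the label *Causal relationship*, and a trained investigator will read it that way. Section 18.7 points events with another reasonable explanation to *Unlikely related* and names underlying illness as an alternative cause under *Possible related*. A temporal relationship is not defined and need not mean any onset after application. Site staff are trained in event reporting (8.4), and the reporting forms, which may carry guidance, are not in the file. The inclusive cut-off is coherent, so 18.2 may be a broad threshold, not a contradiction. Over-grading also errs towards inclusion: true device effects would be mixed with others, not lost.

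Much of this stands. Training and forms may reduce the problem, and the inclusive reading is reasonable. But relying on the label concedes that the definition beneath it is wrong, and the inclusive reading is nowhere stated. If it is adopted, it leaves *Not related* unusable for SAEs during wear.

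A reader might infer more: that, for SAEs explained by illness, the literal wording turns all of them into SADEs while a causal reading turns none into SADEs. The documents do not support that contrast. A causal reader would choose *Unlikely related*, which 18.2 lists among the ADE grades, so both readings can give a SADE. The contrast appears only if *Unlikely related* is first excluded from ADEs. Section 10.1 also does not specify a SADE or USADE proportion, so no planned estimate would shift.

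**Conclusion.** The definitions are wrong as written. For an SAE during wear with another reasonable explanation, 18.7 allows both *Unlikely related* and *Definitely related* and excludes *Not related*. Separately, 18.2 and 18.7 leave ADE, SADE and USADE status without a stated cut-off.

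The effect is on classification and interpretation. The *Not related* fault reaches in principle every SAE with onset during wear. The documents give no expected number of SAEs, so no count or rate can be put on it. A reader should not infer that the safety counts are wrong or that SAE reporting would fail, because neither depends on the grade (step 4).

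Two assumptions are needed: that onset during wear, or close to a scheduled lift, is a temporal relationship, and that the forms and training do not already correct the definitions. Confidence is high on the wording and lower on how far actual grading would be affected. The change should be made because the grade is what separates device from illness in a study without a control arm.

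**What to change.** (a) In 18.7:

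- Require for the top grade, besides timing, that no other cause reasonably explains the event.
- Allow *Not related* when the event is clearly due to another cause, whatever its timing.
- Make the grades mutually exclusive. *Probable related* already uses the lack of another explanation, and *Unlikely related* the presence of one, so the text must say what separates each from the end grade next to it.
- State whether the scale covers all adverse events or only SAEs.

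(b) Reconcile 18.2 with 18.7 on whether *unlikely related* events are ADEs. State which grades count as device-related for ADE, SADE and USADE, and what follows for the 24-hour reporting in 18.7 and the follow-up in 18.5 of non-serious events.

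The cost is wording in two sections and matching guidance on the event forms, with no new patients or visits. There are downsides. *Not related* will rest more on investigator judgement, and the choice on *unlikely related* changes how many non-serious events fall under the ADE rules, so it should be made openly. Section 5.9 planned the last subject's completion for December 2022. Any SAEs already graded would need regrading under the revised definitions, with both grades kept and reported.
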